
### **B6.** Potential Obstacles and Solutions

**B6a. Timing of Data Collection**. The evaluation's launch will be reliant on identification of low-performing VAs and WHS's introduction of EBQI plans with facility and VISN leadership. Once navigated, we will brief leaders of participating VAs regarding the evaluation, work with locally identified contacts, and begin sample development (KS, provider/staff). KS interviews will begin as soon as practicable, as will baseline administrative data extraction. Provider/staff surveys, however, will have to undergo review by the National Center for Organizational Development's Organizational Assessment Sub-Committee (OASC) as the evaluation meets the criteria of VA employees across 10+ sites. While no FY17 blackout dates have yet

been published, we will be required to accommodate them. As with prior work, we will also submit the surveys for national Union review, with a 30-day review period.

**B6b. Timing and Unit of Randomization**. The EBQI contractor was recently approved (8/22/16), enabling an early start on site selection. WHS has agreed to allow us to randomly allocate up to eight VA facilities of the 24 low-performers in Year 1, up to eight VAs of the remaining 16 in Year 2, with the remainder getting EBQI exposure in Year 3. If the EBQI contractor does not meet contract deliverables, evaluation activities may be delayed to accommodate their processes. Fortunately, the contractor (Atlas Research) has a strong track record with VA and specifically WHS. We plan to proceed with the evaluation even if not all contracted-for activities occur, enabling us to still address our evaluation aims. Low-performing facilities may also suffer from leadership gaps, provider and staff burnout, and other structural and management issues that may complicate their engagement in evaluation activities. We have experience working with VHA, VISN and VAMC leaders in multilevel research and evaluation, but will consider site replacement, depending on the circumstances.

**B6c. Survey Feasibility and Subject Burden.** Based on prior experience, we anticipate high participation rates in the KS interviews (96% completed interviews in the WH PACT trial), chiefly in light of the caliber of interviewers, the comfort and trust they routinely engender, and the open offer to not record sensitive dialogue as needed. Even so, we plan on 30-minute rather than 60-minute interviews to reduce subject burden while also increasing feasibility of rapid deliverable generation. We have achieved 85-100% response rates (RRs) on our past PC, WH and MH organizational surveys,  but lower rates for subspecialists (e.g., average 60% RR for cardiology, neurology, oncology chiefs). We have divided the organizational surveys that will be used here into modules to minimize respondent burden for any one key informant, while ensuring that the most knowledgeable respondent is asked. We anticipate the lowest RRs for providers and staff, given competing demands, but will use approaches similar to those used by the VISN 22 PACT Demo Lab (>60% RR), including local leader survey endorsements, incentives/perquisites (if available), and aggregated feedback.

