## **B3. Study Population and Sampling Strategy**

# Figure 1. Staged EBQI Implementation

In the first 30 days of FY17, with input from WHS and the evaluation team, the EBQI contractor will analyze prior site visit assessment data (Booz-Allen-[name] FY16 report), local VA facility self-assessment data (WATCH) (**Appendix 2**), and selected performance measures to identify the lowest-performing VAs (bottom 25-30%) of previously assessed sites nationwide and by VISN. In FY17Q1, WHS will make the final site selection decision (n=24 VA facilities) that will be the focus of EBQI implementation and evaluation.

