B5b. Quantitative Analyses (Aim #2). To assess effectiveness of EBQI implementation on comprehensive care achievement, we will use data from the organizational surveys (§B4b), provider/staff surveys (§B4c) and administrative data on quality and patient experiences (§B4d). Dependent Variables: We will examine multiple outcome measures as dependent variables: 1) multiple individual measures of comprehensive care achievement, including levels of WH service availability (as noted in VHA Handbook 1330.01), integration of and access to gender-specific and MH care, and other related measures that capture different domains of comprehensiveness; 2) gender-sensitive care delivery, including organizational and provider/staff level measures; and 3) quality of care and patient experience measures. For comprehensive care achievement, we will include as dependent variables the individual measures, and we will also examine approaches to creating an aggregated ordinal score of the individual measures. We will prioritize the final set of dependent variables in consultation with WHS. Independent Variables: The primary regressors of interest will be EBQI exposure (i.e., level of implementation) and time. We will examine the potential moderating effects of practice context and provider/staff knowledge/attitudes (e.g., determine EBQI effects in high vs. low leadership support sites). We will use multiple linear or logistic regression to evaluate EBQI effectiveness. Where appropriate we will adjust for covariates, account for clustering of patients by site, and mitigate bias due to non-response or loss to follow-up through the use of enrollment/attrition weights. Covariates used for adjustment will include patient factors (e.g., facility casemix, proportion of WVs seen), provider/staff factors (e.g., DWHP availability, readiness), and organizational factors (e.g., resource sufficiency, facility size). Clustering by site will be accounted for by fitting hierarchical regression models with random intercepts for the sites (e.g., using SAS PROC Mixed). We will evaluate the goodness-of-fit of a given regression model using standard diagnostics (e.g., Mallow's statistic (Cn)). To adjust for potential non-response bias and loss to follow-up over time for the provider/staff survey samples, we will apply enrollment weights using available characteristics of eligible providers/staff and attrition or "inverse probability of inclusion" weights estimated using an appropriately specified logistic regression model. We will use multiple imputation methods to replace missing values among covariates with hot-deck methods used for imputation as needed. We will estimate site-level effects using the hierarchical regression models with random intercepts for sites. While our sample of sites (24) is small for the estimation site-level effects. EBQI trials of fewer sites have noted significant effects.

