#### D. MANAGEMENT PLAN AND TIMELINE

**D1. Management Plan**. The core team ([name], [name], [name], [name], [name], [name], [name]) will meet weekly, with biweekly Aim-specific meetings focused on evaluation sub-aims (e.g., KS interviews). Monthly

WHS calls already underway will continue throughout the PEC's evaluation period, with additional emails and calls arranged to meet Partner information needs and obtain WHS review/input. We will also participate in regular WHS calls with the EBQI contractor (see *Organizational Chart* in **Appendix 7**). Drs. [name] and [name] will attend 1-2 of the initial in-person EBQI meetings and join initial site engagement calls.

**D2. Timeline/Deliverables**. We will deliver written quarterly reports and briefings to WHS throughout the evaluation, consistent with current practices in annual WHS Memoranda of Understanding (MOUs). The FY17 MOU has already been finalized and will be signed before QUERI PEC review but for a reduced scope of work. Deliverables (below) will be appended to the MOU in Quarter 1 (Q1) if the PEC is awarded.

**FY17:** In Q1, we will work with WHS and the EBQI contractor to finalize operational criteria for classifying low-performing VA facilities. We will review the draft KS interview guide (**Appendix 3**) and provider/staff surveys (**Appendix 5**) with WHS, incorporating WHS and other subject matter experts' feedback as requested. WHS has already approved the organizational survey modules for FY17 (**Appendix 4**); these will be fielded in Q1. WHS will launch facility leadership introductions (including notification of evaluation plans), affirming participation, after which we will randomly allocate sites to EBQI (n=8) or waitlisted control (n=16). We will support contractor training in EBQI technical specifications in collaboration with WHS, document training, and develop a template for use in monitoring EBQI procedures used.

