In Q2, WHS and the EBQI contractor will identify local champions and evaluation contacts for our use in identifying KS and launching baseline interviews across all sites. Organizational survey data will be cleaned and a report of initial frequencies provided to WHS. Provider/staff surveys will be submitted to OASC when released by WHS, after which we will submit them for national Union review; endorsement letters will be drafted for WHS review, and adapted to fit local contexts and needs, while we simultaneously obtain and begin validating sample lists. We will also pull and analyze the administrative data for participating sites.

In Q3, we will deliver KS summaries to WHS, while beginning to conduct the more in-depth ATLAS.ti analyses. We will finalize the provider/staff surveys following OASC and Union review, program them in REDCap, and launch survey administration by the end of Q3. We will conduct an organizational analysis of the 24 participating low-performers compared to higher performers of similar complexity.

In Q4, we will provide results for Aim #1 (barriers/facilitators) to WHS in the form of presentations and summary reports for each group of sites. We will finish provider/staff survey follow-up, with concurrent data cleaning and quality checks, followed by analysis and reporting to WHS of baseline evaluation findings for Aim #2. We will generate an annual report for WHS, summarizing evaluation findings across all data sources for FY17.

**FY18**: In Q1, we will randomly allocate the next 8 VA facilities to EBQI, update the KS sample, and launch the second wave of KS interviews, focusing first on baseline for newly allocated EBQI VAs. We will restart the OASC and national Union review procedures, adapting to FY18 blackout dates, and launch the second wave of the organizational surveys.

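### Site replacement is left open with no cut-off at random allocation, so replacing allocated sites unevenly by Group could bias the EBQI comparison in either direction

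*Combined protocol and SAP*

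**What the plan says.** The replacement provision is in B6b (Timing and Unit of Randomization). It starts from the observation that "Low-performing facilities may also suffer from leadership gaps, provider and staff burnout, and other structural and management issues", which could make engagement in evaluation activities harder. The team has experience of working with such leaders, "but will consider site replacement, depending on the circumstances". Nothing in the available text says when replacement may happen, on what grounds, who decides, where the new site comes from, or how the old and new sites are analysed.

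The related provisions are:

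- **Selection (B3).** "WHS will make the final site selection decision (n=24 VA facilities"), in FY17 Q1.
- **First allocation (D2, FY17 Q1).** Leadership introductions come first, "affirming participation, after which we will randomly allocate sites to EBQI (n=8) or waitlisted control (n=16"). B6b describes the same draw: "randomly allocate up to eight VA facilities of the 24 low-performers in Year 1".
- **Second allocation (D2, FY18 Q1).** "we will randomly allocate the next 8 VA facilities to EBQI". The last 8 sites start in Year 3.
- **Analysis (B5b).** The main regressors are "EBQI exposure (i.e., level of implementation) and time". There is no rule that sites are analysed as allocated. The non-response and attrition weights are specified for the provider/staff survey samples, not for lost or replaced facilities.

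**The concern.** The design rests on random order of launch across 24 facilities (B2). Replacing a facility after its order has been drawn is selection after randomisation, and with 8 sites per Group one replacement changes 12.5% of a Group (1/8).

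The reasons that would prompt replacement are ones the plan itself links to outcome. B5b names leadership support as a possible effect moderator, and readiness and resource sufficiency as covariates.

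Timing adds to the risk. In D2, only the organizational survey is fielded in FY17 Q1. Baseline stakeholder interviews launch in Q2 and provider/staff surveys by the end of Q3. A site that engages poorly would mostly be recognised once its arm is known.

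Replacement would also take out the hardest facilities, although the stated aim is effectiveness in low performers.

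**Working it through.** The plan gives no effect size, standard deviation, within-site correlation or power, so it has no figure to reproduce. The allocation counts agree: 24 − 8 = 16, 16 − 8 = 8, 3 × 8 = 24. What follows is an illustration, with its assumptions marked.

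**Inputs**

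- From the plan: 24 sites, three Groups of 8, three yearly waves. Exposure by wave is 0,1,1 (Group 1), 0,0,1 (Group 2) and 0,0,0 (Group 3, whose last planned survey wave is taken as before any effect).
- Assumed: the least-engaged 1 or 2 of 8 sites are replaced by average sites; correlation 0.5 between engagement and outcome change; within-site correlation ρ of 0.5 or 0.7; site-level outcome SD of 1; no replacement among comparison sites.

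**Step 1: shift in mean engagement.** The two lowest expected normal order statistics for n = 8 are −1.42 and −0.85. Replacing one site shifts the Group mean by 1.42/8 = 0.178 SD. Replacing two shifts it by (1.42 + 0.85)/8 = 0.284 SD.

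**Step 2: shift in outcome change.** Multiplying by 0.5 gives 0.089 and 0.142 SDs of change. The SD of change is √(2(1 − ρ)), which is 1.000 at ρ = 0.5 and 0.775 at ρ = 0.7. In site-level SDs the shifts are 0.089 and 0.142 (ρ = 0.5), and 0.069 and 0.110 (ρ = 0.7).

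**Step 3: effect on the estimate.** I used generalised least squares with wave effects and a random site intercept. The standard error (SE) of the EBQI effect is 0.274 at ρ = 0.5 and 0.224 at ρ = 0.7. The weights that the estimator gives to Group means at waves 1, 2 and 3 are:

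- ρ = 0.5: Group 1 −0.300, 0.500, 0.100; Group 2 0, −0.400, 0.400.
- ρ = 0.7: Group 1 −0.389, 0.500, 0.056; Group 2 0, −0.444, 0.444.

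A shift in Group 1 after launch (waves 2 and 3) therefore enters with weight 0.600 or 0.556. A shift in Group 2 after launch (wave 3) adds 0.400 or 0.444, so the two together enter with weight 1.

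| Replaced | ρ | Bias, SD (1 site; 2 sites per Group) | Bias, SE |
|---|---|---|---|
| Group 1 only | 0.5 | 0.053; 0.085 | 0.19; 0.31 |
| Group 1 only | 0.7 | 0.038; 0.061 | 0.17; 0.27 |
| Groups 1 and 2 | 0.5 | 0.089; 0.142 | 0.32; 0.52 |
| Groups 1 and 2 | 0.7 | 0.069; 0.110 | 0.31; 0.49 |

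An equal shift in all three Groups gives zero, because the weights sum to zero at each wave. The same shift in Group 3 alone gives −0.17 to −0.31 SE. If engagement affects the outcome level rather than change, replacement in Groups 1 and 2 gives only 0.07 to 0.16 SE, because the site intercept absorbs most of it.

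**Range for the assumed 0.5.** Bias is proportional to this correlation. At 0.3 (factor 0.6) and 0.7 (factor 1.4), Group 1 only runs from 0.17 × 0.6 = 0.10 to 0.31 × 1.4 = 0.43 SE. Groups 1 and 2 run from 0.31 × 0.6 = 0.19 to 0.52 × 1.4 = 0.73 SE.

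**Cross-check on direction.** A simulation under no true effect compared 8 EBQI with 16 waitlisted sites in Year 1, with one outcome per site, no baseline adjustment, a two-sided 5% t-test, and 40,000 runs per setting.

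- Replacing 1 or 2 of the 8 EBQI sites only: bias of +0.06 to +0.20 SD over correlations 0.3 to 0.7. The false-positive rate favouring EBQI rises from about 2.5% to between 3.3% and 6.7%.
- Replacing the same share in both arms: −0.005 to −0.011 SD.
- Replacing 2 or 4 of the 16 waitlisted sites only: −0.06 to −0.21 SD, against EBQI.
- Correlation 0, or no replacement: no bias beyond simulation error.

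**The case against.** A reader might infer that the plan means to remove struggling EBQI sites, or that the comparison is biased in favour of EBQI. The documents support neither.

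- The sentence says replacement will be considered, not that it will happen.
- It concerns low-performing facilities in general and "structural and management issues that may complicate their engagement in evaluation activities", not EBQI uptake. Waitlisted sites also take part in interviews and surveys (B4a to B4c), so they could be replaced too.
- B6b says the evaluation goes ahead even if some contracted EBQI activities do not occur, which argues against dropping a site for weak delivery.
- Affirming participation before allocation gives an early chance to screen out unwilling sites.

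All of this stands, and it means that the direction of bias is not fixed. It does not close the gap, because replacement is not confined to the screening step and no as-allocated rule protects the comparison afterwards.

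That active sites are the more exposed arm is an inference, though a reasonable one. They carry stakeholder meetings, QI team meetings and collaboration calls (A6), and D2 extends their interview sample to match EBQI targets. Waitlisted sites do not have this load while they wait.

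**Conclusion.** The concern holds as a risk that the plan leaves open. Most of the engagement problems that would prompt replacement would show after the FY17 Q1 allocation, and uneven replacement by Group could then bias the effect either way, plausibly towards EBQI.

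Under the stated assumptions the size is modest: 0.04 to 0.09 SD (0.17 to 0.31 SE) if only Group 1 sites are replaced. The higher range of 0.31 to 0.52 SE needs the same replacement in Groups 1 and 2, that is 2 to 4 sites in all, with none among the comparison sites. The correlation, the number replaced and the choice of the least-engaged sites are assumptions; the plan supplies none of them. The point merits a change because the protection is cheap and the randomisation is the design's main strength.

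**What to change.** 1. **B6b.** Allow replacement only before the FY17 Q1 (Year 1) allocation, while participation is being affirmed. Name this draw, since there are two: replacing a waitlisted site between them leaves the Group 2 versus Group 3 draw intact but alters the Group 1 versus waitlist comparison. After it, every facility keeps its allocation.
2. **B5b.** Make the effectiveness comparison by assigned launch date, whatever a site's engagement. Treat level of implementation as a secondary analysis.
3. **Disengaged sites.** Keep them in through measures derived from the Corporate Data Warehouse and other routinely collected data. This does not recover the provider/staff survey outcomes (Aim 2b), and WATCH still depends on facility self-report.
4. **Late substitution.** If VA Women's Health Services (WHS) nevertheless substitutes a site after allocation, leave the substitute out of the effectiveness analysis and report the replacement by Group and reason.

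The cost is mainly wording, plus agreement from WHS, which controls site selection. The downside is that sites with weak uptake stay in the EBQI Groups, so the estimated effect may be smaller.

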**C4. Local Resources Supporting Evaluation Team.** The PEC will reside organizationally within CSHIIP, while benefiting from the infrastructure, professional networks, and research teams of the VA WHRN ([name], [name], [name], PIs), WH CREATE ([name], Director), EMPOWER QUERI Program ([name], Director), and the Office of Health Equity PEC ([name], Co-I). This collaborative context will enable cross-coverage and technical support to PEC team members. CSHIIP is heavily leveraged by partner-funded initiatives as well as two QUERI Programs (EMPOWER and Care Coordination), providing an unusually strong environment of implementation scientists brought together in biweekly work-in-progress seminars. CSHIIP has also launched Implementation and Improvement Cores supporting development and testing of dissemination tools and EBQI implementation strategies in the context of VAMC and VISN level initiatives.

#### D. MANAGEMENT PLAN AND TIMELINE

**D1. Management Plan**. The core team ([name], [name], [name], [name], [name], [name], [name]) will meet weekly, with biweekly Aim-specific meetings focused on evaluation sub-aims (e.g., KS interviews). Monthly

WHS calls already underway will continue throughout the PEC's evaluation period, with additional emails and calls arranged to meet Partner information needs and obtain WHS review/input. We will also participate in regular WHS calls with the EBQI contractor (see *Organizational Chart* in **Appendix 7**). Drs. [name] and [name] will attend 1-2 of the initial in-person EBQI meetings and join initial site engagement calls.

**D2. Timeline/Deliverables**. We will deliver written quarterly reports and briefings to WHS throughout the evaluation, consistent with current practices in annual WHS Memoranda of Understanding (MOUs). The FY17 MOU has already been finalized and will be signed before QUERI PEC review but for a reduced scope of work. Deliverables (below) will be appended to the MOU in Quarter 1 (Q1) if the PEC is awarded.

**FY17:** In Q1, we will work with WHS and the EBQI contractor to finalize operational criteria for classifying low-performing VA facilities. We will review the draft KS interview guide (**Appendix 3**) and provider/staff surveys (**Appendix 5**) with WHS, incorporating WHS and other subject matter experts' feedback as requested. WHS has already approved the organizational survey modules for FY17 (**Appendix 4**); these will be fielded in Q1. WHS will launch facility leadership introductions (including notification of evaluation plans), affirming participation, after which we will randomly allocate sites to EBQI (n=8) or waitlisted control (n=16). We will support contractor training in EBQI technical specifications in collaboration with WHS, document training, and develop a template for use in monitoring EBQI procedures used.

In Q2, WHS and the EBQI contractor will identify local champions and evaluation contacts for our use in identifying KS and launching baseline interviews across all sites. Organizational survey data will be cleaned and a report of initial frequencies provided to WHS. Provider/staff surveys will be submitted to OASC when released by WHS, after which we will submit them for national Union review; endorsement letters will be drafted for WHS review, and adapted to fit local contexts and needs, while we simultaneously obtain and begin validating sample lists. We will also pull and analyze the administrative data for participating sites.

In Q3, we will deliver KS summaries to WHS, while beginning to conduct the more in-depth ATLAS.ti analyses. We will finalize the provider/staff surveys following OASC and Union review, program them in REDCap, and launch survey administration by the end of Q3. We will conduct an organizational analysis of the 24 participating low-performers compared to higher performers of similar complexity.

In Q4, we will provide results for Aim #1 (barriers/facilitators) to WHS in the form of presentations and summary reports for each group of sites. We will finish provider/staff survey follow-up, with concurrent data cleaning and quality checks, followed by analysis and reporting to WHS of baseline evaluation findings for Aim #2. We will generate an annual report for WHS, summarizing evaluation findings across all data sources for FY17.

**FY18**: In Q1, we will randomly allocate the next 8 VA facilities to EBQI, update the KS sample, and launch the second wave of KS interviews, focusing first on baseline for newly allocated EBQI VAs. We will restart the OASC and national Union review procedures, adapting to FY18 blackout dates, and launch the second wave of the organizational surveys.

In Q2, we will continue with KS interviews, including WHS and EBQI contractor interviews and extending the KS sample to accommodate EBQI targets in Group 1 (e.g., MH leads). We will update the provider/staff survey sample lists, and work with site-level evaluation contacts on sample validation and updated cover letters as needed (i.e., to accommodate leadership changes). By the end of Q2, we will deliver KS summaries and organizational survey findings. We will launch the second wave provider/staff surveys in Q2. We will also pull a second year of administrative data, and provide WHS with a summary report on changes.

In Q3, we will finish the provider/staff survey wave, clean the data and deliver an initial summary report. KS analysis will continue. KS contrasts between Year 1-2 will be reported, in addition to early findings regarding Aim #3 contextual factors and implementation processes based on both waves. Additional organizational analyses with linked administrative data for Aim #2 will also be reported (e.g., variations in resource sufficiency by large and small low-performers).

In Q4, organizational changes based on KS interviews and organizational surveys between Years 1 and 2 overall and by EBQI vs. waitlisted controls will be reported to WHS. We will deliver a second annual report for WHS, summarizing findings across evaluation data sources for FY18, with notable FY17 comparisons.

**FY19**: In Q1, the EBQI contractor will launch EBQI in the remaining low-performing VA facilities. We will again update the KS sample as needed, and launch the third and final wave of KS interviews and again

extend the KS sample to accommodate EBQI targets in Groups 1 and 2 that will have had two and one year of EBQI, respectively. We will start with the baseline KS interviews for Group 3, followed by the KS followup interviews for Groups 1 and 2, which may carry over into Q2. We will again repeat OASC and Union review, and launch the third and final organizational survey wave.

In Q2, we will complete the KS interviews, and initiate rapid KS analysis. We will update the provider/staff sample for the third wave, repeat sample validation steps with participating sites, and prepare endorsement letters once again, and launch the survey by the end of Q2. By the end of Q2, we will also provide WHS with the third wave of KS summaries and an organizational survey summary in the quarterly report.

In Q3, we will continue conducting the more detailed qualitative coding for the annual report and completion of Aim #3 by Q4. We will deliver a summary of organizational changes over all three survey waves to WHS, as well as an initial provider/staff survey summary for the third and final wave. KS contrasts by year will be highlighted as well. We will pull and analyze administrative data, aiming for as many months of data as possible for the summative evaluation as part of Aim #2.

In Q4, we will report time trends related to Aim #1 (developmental evaluation), as well as summative results for Aim #2 (progress-focused evaluation) and Aim #3 (implementation-focused and interpretive evaluation) to WHS. We will include an appraisal of EBQI's potential utility for related WHS initiatives and its sustainability and spread.

In addition to these partner-focused deliverables, we plan to submit the protocol to *Implementation Science* for publication, as we did with the WH PACT EBQI trial, and pursue other traditional dissemination routes through scientific journals and presentations. We will also prepare brief summaries for WHS e-newsletters to the field when appropriate, provide briefings to participating sites' leadership at the VAMC and VISN levels on findings over the course of the evaluation, and offer national briefings to other relevant Program Offices (e.g., MHS, PC, NCP, OPCC&CT) based on evaluation findings and WHS recommendations and requests. With WHS, we will also disseminate findings to WVs, through existing WV Councils affiliated with WHRN and the WH CREATE, consistent with our Veteran engagement work.

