**A3. Evaluation of Comprehensive Care Policy Implementation.** WHS contracted with a private sector firm from 2010-15 to gauge progress towards full Handbook implementation through site visits that included interviews with approximately 20 individuals/groups, case discussions, facility tours, and a review of program-related documents. Each VAMC's capabilities were then scored (from "needs development" to "highly developed") through focused team consensus sessions across 33 Handbook-related domains. Site visits concluded with closing conferences with leadership, followed by Site Visit Summary Reports and Score Cards for each site. WHS received dashboard updates for distinctively high- and low-end performers on program components and capabilities by facility and VISN.

Major problematic findings included gaps in organizational structure (e.g., WV Program Managers being assigned collateral duties, precluding focus on policy-mandated roles and responsibilities), inadequate oversight or planning, major gaps in privacy/security in exam rooms, limited cross-coverage for key WH roles, environments not welcoming to women, gaps in comprehensive care in community-based outpatient clinics, staffing insufficiency (including below-standard staffing ratios, high panel sizes, limited WH experience/training), and limited efforts to improve cultural competency and gender sensitivity of staff.

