# **B2. Evaluation Design**

The choice of a dynamic waitlisted design is based on WHS's plans for staged EBQI implementation at no more than eight VA facilities per year for the next three years for a total of 24 facilities. This randomized "roll-out" implementation design has very good statistical properties, including higher power than traditional

wait-listed designs and less vulnerability to external, uncontrolled factors. EBQI implementation will commence in Year 1 (FY17) in eight randomly selected facilities (Group 1), with the remaining 16 facilities serving as waitlisted controls. In FY18, eight of these waitlisted controls will be randomly selected for EBQI implementation (Group 2), leaving the remaining eight as waitlisted controls in FY18, which will begin EBQI implementation in Year 3 (Group 3).

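### The allocation of the 24 facilities is described without any restriction on baseline performance, and baseline performance is not a named covariate, although the selection data exist before the draw

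*Combined protocol and SAP*

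**What the plan says.** **Selection (B3).** In the first 30 days of FY17 the contractor analyses earlier site-visit assessments, "local VA facility self-assessment data (WATCH") and selected performance measures "to identify the lowest-performing VAs (bottom 25-30%) of previously assessed sites nationwide and by VISN". Then "WHS will make the final site selection decision (n=24 VA facilities"). Background section A3 adds that the site visits scored each medical center on 33 domains.

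**Allocation.** B2: "EBQI implementation will commence in Year 1 (FY17) in eight randomly selected facilities (Group 1"); in FY18 "eight of these waitlisted controls will be randomly selected for EBQI implementation (Group 2"), and the last eight start in Year 3. B6b: "WHS has agreed to allow us to randomly allocate up to eight VA facilities of the 24 low-performers in Year 1". D2 puts the first draw after site selection and confirmation of participation: "we will randomly allocate sites to EBQI (n=8) or waitlisted control (n=16"). None of these sections names a stratum, matched set, constraint or minimisation rule.

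**Analysis (B5b).** Hierarchical regression with random site intercepts, adjusting for covariates where appropriate. The organizational examples are resource sufficiency and facility size. The performance data used to choose the sites are not named. B5b itself calls 24 sites small for estimating site-level effects, and no power figure is given.

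**The concern.** The number of randomised units is 24, split 8 v 16 and then 8 v 8, so sizeable chance gaps between launch Groups are to be expected. The data that would limit them are assembled before the draw, but the plan uses them only to pick the sites.

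The usual reply is that each site acts as its own control. A random site intercept deals with differences in level. It does not deal with differences in expected change. The sites are chosen because they score low, and among such sites the lowest may change most, through regression to the mean and room to improve. If so, a gap in baseline score between Groups becomes a gap in expected change, which neither the intercept nor a common time effect absorbs. At stake are a wider error on the EBQI estimate, and the credibility of the plain EBQI v waitlist reports promised to the partner in FY18 Q4.

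**Working it through.** **Inputs.** From the plan: 24 sites; 8 v 16 in FY17; 8 v 8 in FY18; random site intercepts. The plan gives no alpha, power, effect size, SD, within-site correlation or link between score and outcome, so there is no figure of its own to reproduce. Those inputs are assumed below.

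**1. Chance imbalance.** In units of the score's SD among the 24 sites, the SD of the difference in means is sqrt(1/n1 + 1/n2).

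- 8 v 16: sqrt(1/8 + 1/16) = 0.433. P(gap > 0.5 SD) = 2 x P(Z > 0.5/0.433) = 2 x P(Z > 1.155) = 0.248.
- 8 v 8: sqrt(1/8 + 1/8) = 0.500. P(gap > 0.5 SD) = 2 x P(Z > 1.0) = 0.317.

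**2. Effect of restricting the FY17 draw** (20,000 simulated allocations).

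| Allocation | SD of 8 v 16 gap | P(gap > 0.5 SD) |
|---|---|---|
| Unrestricted | 0.43 | 0.25 |
| Two strata of 12 | 0.27 | 0.06 |
| Eight matched triplets | 0.11 | < 0.001 |

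**3. FY17 parallel contrast.** Assumed: effect 1 SD of site means, two-sided 0.05, score-outcome correlation 0.3 / 0.5 / 0.7.

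| Allocation | SD of estimate, score not in model | SD of estimate, score in model | Power, score not in model | Power, score in model |
|---|---|---|---|---|
| Unrestricted | 0.433 / 0.434 / 0.429 | 0.423 / 0.388 / 0.319 | 0.60 / 0.60 / 0.59 | 0.61 / 0.70 / 0.85 |
| Two strata of 12 | 0.419 / 0.396 / 0.361 | 0.415 / 0.376 / 0.311 | 0.60 / 0.60 / 0.61 | 0.63 / 0.72 / 0.86 |
| Triplets | 0.415 / 0.378 / 0.321 | 0.415 / 0.374 / 0.312 | 0.60 / 0.60 / 0.62 | 0.63 / 0.72 / 0.87 |

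Restriction without the score in the model barely moves power, because the unadjusted standard error does not reflect the gain. Most of the power comes from adjustment; restriction adds about 1-2 points. With the score in the model, two strata do about as well as triplets.

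**4. Roll-out, score related to level only.** With random intercepts and 24 sites at four time points, moving from unrestricted to triplet allocation changes the SD of the estimate by between +2% and -4.5%. Monte Carlo error is about 1.6% on each ratio. The intercept does most of the work here.

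**5. Roll-out, score related to change.** With 24 sites, three waves and within-site correlation 0.5 or 0.7, the table gives variance relative to unrestricted allocation without the score. R2 is the assumed share of site-level change that the score explains. Ranges run across the set-ups simulated.

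| R2 | Triplets plus score in model | Reduction |
|---|---|---|
| 0.10 | about 0.90-1.00 | 0-10% |
| 0.25 | 0.71-0.84 | 16-29% |
| 0.40 | 0.57-0.72 | 28-43% |

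At R2 0.25, adjustment alone gives 0.74-0.87 and triplets alone 0.73-0.86, so the two overlap heavily. In one set-up, adding triplets to adjustment moved the ratio from 0.81 to 0.74 and from 0.87 to 0.80, a saving of 1 - 0.74/0.81 = 9% and 1 - 0.80/0.87 = 8%. In another it moved from 0.74 to 0.71 (4%) and from 0.79 to 0.80 (none). At R2 0.10 and 0.40 the added saving was about 3% and 1-3%.

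With 3,000 replicates per arm, Monte Carlo error on a variance ratio is about sqrt(2/3000 + 2/3000) = 0.037 if the runs are independent. The gain at R2 0.10 is therefore hard to tell from none.

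**The case against.** Several points on the other side stand.

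- **The method is unstated.** The plan never says that randomisation is simple. Absence of restriction is read from sections that say only that sites are drawn at random, so the first request is that the method be stated.
- **No single score exists yet.** B3 lists three sources, D2 leaves the operational criteria to be finalised in FY17 Q1, and B5b leaves the outcomes to be prioritised. A score that predicts change in service availability may say little about glycemic control. All 24 sites come from the lowest 25-30%, and this narrow range may weaken any link.
- **The covariate lists are examples.** Baseline performance is not excluded; it is just not pre-specified.
- **Fixed matched triplets would be fragile.** B6b allows fewer than eight sites a year and possible site replacement.

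Stronger readings are tempting, and the documents do not support them. A reader might infer that imbalance biases the EBQI estimate. It does not: over repeated randomisation the estimator is unbiased, and the loss is in precision and in how convincing one realised allocation looks. A reader might also credit the allocation method with the whole gain. At ratios of 0.84 and 0.76, that gain equals 24/0.84 - 24 = 4.6 and 24/0.76 - 24 = 7.6 extra sites, but it belongs to allocation and adjustment together. On a 9% saving, allocation's own addition is about 24/0.91 - 24 = 2.4 sites at most. Nor is the change free, since the score uses degrees of freedom.

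The own-control argument stands for differences in level (step 4), not for score-dependent change (step 5).

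**Conclusion.** The concern holds as a worthwhile, low-cost improvement and not as a flaw that undermines the design. Without restriction there is about a 1 in 4 chance (FY17) and a 1 in 3 chance (FY18) of a gap over 0.5 SD on any given baseline score. That part is arithmetic and needs only the plan's site numbers.

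The precision gain rests on an assumed R2 that the documents cannot inform. It runs from negligible at 0.10 to substantial at 0.40, mostly from adjustment. What restriction adds is a few percent of variance and balance that needs no model. Imbalance cannot be undone after the draw, which is the reason to settle this beforehand.

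**What to change.** **B2 and B6b.** State the allocation method. Before the draw, define one baseline performance score from the selection data and allocate within two or three strata of it, or by constrained randomisation. Two strata of 12 fit the planned sequence: four sites from each stratum in FY17, and four of the remaining eight in each in FY18. Three strata would need unequal sizes such as 9, 9 and 6 (3 + 3 + 2 = 8 per Group). A few strata tolerate a short year or a replaced site better than fixed triplets do, and the FY18 draw can stay where it is.

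**B5b.** Name the score and its interaction with time as pre-specified covariates, so that the analysis reflects the allocation.

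**Cost.** A short allocation program on data already assembled, and up to about three parameters with 24 sites (one main effect and two interaction terms for three waves). If the score turns out unrelated to change, those parameters buy balance but little precision.
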